**Table 10. Illustration of Sensitivity Analyses**

$P_u$ for SA4Ag a	$P_u$ for Placebo a			
	0	Observed b	0.5	1
0	Observed VE		MNAR	Best case for SA4Ag
Observed b		MAR		
0.5	MNAR		MNAR	
1	Worst case for SA4Ag			

a.  $P_u = \text{Pr}(\text{PDI is microbiologically confirmed } S \text{ aureus, given clinical criteria met})$ .

b. Observed = the number of microbiologically confirmed PDIs divided by the number of PDIs with sufficient microbiological testing.

Abbreviations: MAR = missing at random; MNAR = missing not at random; PDI = protocol-defined infection; Pr = probability; VE = vaccine efficacy.

The steps in the sensitivity analysis are:

1. Identify suspect PDIs that meet relevant clinical criteria but lack microbiological confirmation because of insufficient microbiological testing.
2. Randomly assign microbiological confirmation = yes to each suspect PDI with probability  $P_u$ , depending on vaccine group, as described in [Table 9](#).
3. Concatenate with confirmed PDIs after all suspect PDIs are randomly assigned.
4. Calculate VE and associated CI (see [Section 8.1.1](#)). The confidence level will be 95% except for the primary endpoint in the PP efficacy population, where the confidence level will be 95.1%. If the sensitivity analyses are performed after the interim analysis, then the confidence level will be 95% except for the primary endpoint in the PP efficacy population, where the confidence level will be 99.7%.
5. Perform the indicated number of simulations. If the  $P_u$  values are combinations of 0 and 1, or if the observed probabilities are used, then exactly 1 iteration is required.
6. Tabulate the proportion of simulations where the lower limit on VE exceeds 0%, 20%, and 30%. The descriptive statistics n, mean, standard deviation, median, minimum, and maximum will also be compiled for both VE and the lower confidence limit.

All realized simulations and VE calculations will be saved for possible submission to regulatory authorities. A separate seed should be used for each MAR and MNAR simulation within each endpoint-population combination.

If the number of suspected PDI cases lacking microbiological confirmation is very small, then all possible enumerations may be substituted for the simulations.

Missing values will not be imputed for any immunogenicity, safety, demographic, or colonization variables. However, immunogenicity values less than LLOQ will be set as  $0.5 \times \text{LLOQ}$  for the analysis.

Subjects who are vaccinated but do not undergo the index surgery will not have a Day 1 visit. Their last day in the study will be labeled Day -1.

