### 7. HANDLING OF MISSING VALUES

Sensitivity analyses for efficacy will be performed if there are suspected PDIs without sufficient microbiological testing to confirm or deny the PDI as microbiologically confirmed *S aureus*. Only the primary and secondary efficacy endpoints will be so analyzed. The suspected PDI cases that meet clinical criteria but lack sufficient microbiological testing will be assigned as confirmed PDI with probability  $P_u$ . The sensitivity analyses will examine a range of  $P_u$  values for each vaccine group.

The ranges of  $P_u$  values are described in [Table 9](#). Simulations are not required for every value. For example, when  $P_u = 0$  in the SA4Ag group and  $P_u = 1$  in the placebo group, then every suspect SA4Ag PDI is considered not to be a PDI and every suspect placebo PDI is considered a confirmed PDI. This is the “best-case” sensitivity analysis for SA4Ag.

The missing-at-random (MAR) analysis uses the observed probabilities ( $P_u$ ) for each vaccine group; SA4Ag's (or placebo's)  $P_u$  will be the number of *S aureus* microbiologically confirmed PDIs divided by the number of PDIs with sufficient nonmissing microbiological testing, limited to subjects in the SA4Ag (placebo) group. The missing-not-at-random (MNAR) analyses use a range of  $P_u$  values that are selected without reference to observed  $P_u$  values.

**Table 9. Range of Probabilities for Sensitivity Analyses on Protocol-Defined Infections that Lack Sufficient Microbiological Confirmation**

Scenario	$P_u = \text{Pr}(\text{PDI is microbiologically confirmed } S \text{ aureus, given SA4Ag vaccination and clinical criteria met})$	$P_u = \text{Pr}(\text{PDI is microbiologically confirmed } S \text{ aureus, given placebo vaccination and clinical criteria met})$	Comments	Simulations
1	0	1	Best -case analysis	N/A
2	1	0	Worst -case analysis	N/A
3	0	0	Observed; missing PDIs not included	N/A
4	1	1	Every suspect PDI is microbiologically confirmed	N/A
5	Observed $P_s^a$	Observed $P_p^b$	MAR	2000
6	0	0.5	MNAR	2000
7	0.5	0	MNAR	2000
8	0.5	0.5	MNAR	2000

a. Observed  $P_s$  = the number of *Staphylococcus aureus* microbiologically confirmed PDIs divided by the number of PDIs with sufficient nonmissing microbiological testing, limited to subjects receiving SA4Ag.

b. Observed  $P_p$  = the number of *S aureus* microbiologically confirmed PDIs divided by the number of PDIs with sufficient nonmissing microbiological testing, limited to subjects receiving placebo.

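### SAP Section 7, step 5 asks for one iteration of the missing-at-random analysis where Table 9 asks for 2000; a single random draw makes the reported VE depend on the seed

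*SAP*

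**What the plan says.** SAP Section 7 (Handling of Missing Values) plans sensitivity analyses for the primary and secondary efficacy endpoints when suspected PDIs meet the clinical criteria but were not tested well enough to confirm or exclude *S aureus*. Each such PDI counts as confirmed with probability Pu, set separately for each arm.

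- On which scenario uses observed values, the text says: "The missing-at-random (MAR) analysis uses the observed probabilities".
- Table 9, scenario 5 (MAR, observed Ps and Pp), lists 2000 simulations. Scenarios 1 to 4, where Pu is 0 or 1 in each arm, list none.
- Step 2: "Randomly assign microbiological confirmation = yes to each suspect PDI with probability" Pu.
- Step 5 opens with "Perform the indicated number of simulations". It then reduces the count to one if the Pu values are combinations of 0 and 1, "or if the observed probabilities are used, then exactly 1 iteration is required".
- Step 6 tabulates how often the lower limit on VE exceeds 0%, 20% and 30%, together with the mean, SD, median and range.
- After the steps: "A separate seed should be used for each MAR and MNAR simulation within each endpoint-population combination".

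**The concern.** Step 5 and Table 9 give different iteration counts for the same scenario, and the lower count does not suit a random procedure. If the observed probabilities lie strictly between 0 and 1, step 2 is a random draw for each untested PDI, and one pass yields one arbitrary realisation. The step 6 proportion could then only be 0 or 1, and the SD would be undefined.

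MAR is the only one of the eight scenarios that uses the trial's own confirmation rates. SAP Table 17 applies the methods to four endpoints in three populations, which makes the 12 sets of analyses counted in SAP Section 8.2.1. Two programmers, one following step 5 and one following Table 9, would produce different outputs. Section 7 also foresees that these results may be submitted to regulators.

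**Working it through.** **Can the texts be reconciled?** The step 5 clause might have been meant for scenario 3, which Table 9 labels "Observed; missing PDIs not included". But scenario 3 has Pu = 0 in both arms, so the first half of the same sentence (combinations of 0 and 1) already covers it. The only scenario left for the observed-probability clause is scenario 5, to which Table 9 assigns 2000. Random assignment in step 2, the distribution summaries in step 6 and the seed rule all fit repeated simulation.

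**Inputs from the documents.** SAP Section 8.1.1: with x SA4Ag cases of n and p = x/n, VE = 1 − p/(1 − p), with Clopper-Pearson limits on p transformed in the same way. SAP Section 7, step 4: confidence level 95.1% for the primary endpoint in the per-protocol population at the final analysis, and 99.7% after the interim.

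**Reproducing the plan's figure.** For 14 of 48, VE = 1 − 14/34 = 58.8%, with 95.1% limits of 21.0% and 79.6%, as in Protocol Table 15.

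**Assumed inputs.** The documents give neither the number of untested PDIs (m per arm) nor the observed Pu. I took the success boundary of 14 against 34 as the base, with equal m and equal Pu in the two arms. In one draw the cases become 14 + A and 34 + B, with A and B independent Binomial(m, Pu), and VE = 1 − (14 + A)/(34 + B). All outcomes were enumerated exactly.

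**Smallest case, m = 1.** There are four possible draws:

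| A, B | VE | Lower 95.1% limit |
|---|---|---|
| 0, 0 | 1 − 14/34 = 58.8% | 21.0% |
| 0, 1 | 1 − 14/35 = 60.0% | 23.6% |
| 1, 0 | 1 − 15/34 = 55.9% | 16.6% |
| 1, 1 | 1 − 15/35 = 57.1% | 19.3% |

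The limit exceeds 20% only when A = 0, which has probability 1 − Pu, or 50% at Pu = 0.5.

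**Larger m, Pu = 0.5, base 14 against 34:**

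| Untested per arm | VE from one draw (central 95%) | Chance that lower limit exceeds 20% | SD of one draw (points) |
|---|---|---|---|
| 2 | 52.9% to 61.1% | 37.5% | 2.2 |
| 5 | 48.6% to 61.1% | 32.4% | 3.4 |
| 6 | 47.2% to 60.5% | 28.7% | 3.7 |
| 10 | 42.1% to 60.0% | 17.4% | 4.5 |

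For m = 6, the 28.7% becomes 37.8% at Pu = 0.3 and 14.4% at Pu = 0.7.

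**With 2000 iterations.** The Monte Carlo standard error of the mean VE is SD/√2000. For m = 6 and Pu = 0.5 that is 3.65/44.7 = 0.08 points.

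**Away from the success boundary.**

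- Base 11 against 37, m = 6, Pu = 0.5: VE 59.0% to 71.1%, with the lower limit above 20% in 99.8% of draws.
- Base 11 against 13 (the third futility threshold, 11 of 24 in SAP Table 1), 99.7% level, Pu = 0.5: VE 0% to 26.7% for m = 2 and about −7% to 29% for m = 6. No draw has a lower limit above 0%; for m = 6 the best is about −85%.

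**The case against.** The strongest reply is that this is a stray clause. Table 9, the opening of step 5, step 2 and the seed rule all point to 2000, so a careful programmer would probably choose 2000. That is fair as a prediction, but the clause is explicit, current text and the plan has no rule for which statement prevails.

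Other points limit the weight:

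- The analysis is run only if untested PDIs exist, and it has no part in the decision rule. SAP Section 4.2 rests efficacy conclusions on the interim or final analysis. The best-case and worst-case scenarios bound any MAR draw and do not depend on a seed.
- Nothing in the SAP ranks MAR above the other seven scenarios.
- If untested PDIs are very few, "then all possible enumerations may be substituted for the simulations". This would remove the seed dependence, but it is optional, sets no threshold, and does not override step 5.
- The 14 against 34 base lies on the success boundary, where a small shift moves the lower limit across 20%. SAP Section 8.1.3.5 records that the study met futility at the interim and ceased enrollment, so that base is illustrative. Near the futility boundary no conclusion would turn on the draw, although the reported estimate still would.
- A one-result scenario also gives a step 6 proportion of 0 or 1 in scenarios 1 to 4. There the result is deterministic, so nothing is lost. For MAR, the spread that step 6 is meant to describe would be lost.

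These points reduce the consequence. They do not remove the contradiction.

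**Conclusion.** The concern holds: step 5 is wrong as written. It asks for a single iteration of a random procedure to which Table 9 gives 2000, and no reading of the clause reconciles the two. Followed literally, the MAR estimate depends on the seed. Under the assumptions of 14 against 34 confirmed, equal numbers of untested PDIs per arm and Pu = 0.5, one draw spans about 8 points of VE with 2 untested per arm (61.1 − 52.9 = 8.2) and about 13 with 6 (60.5 − 47.2 = 13.3). Near the success boundary the draw alone can decide whether the lower limit passes 20%. With one untested PDI per arm the whole range is about 4 points (60.0 − 55.9 = 4.1). If both observed probabilities happened to be 0 or 1, one iteration would suffice. The primary analysis is unaffected. This should be corrected, but it does not threaten the trial's conclusion.

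**What to change.** In SAP Section 7, step 5, delete the second condition, the one on observed probabilities, so that one iteration applies only when both Pu values are 0 or 1. MAR then follows the 2000 simulations in Table 9, or full enumeration where Section 7 already allows it. Table 9, step 6 and the seed rule need no change. The cost is one SAP clause and negligible computing.

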## **8. STATISTICAL METHODOLOGY AND STATISTICAL ANALYSES**

### **8.1. Statistical Methodology**

#### **8.1.1. Methodology for Efficacy Endpoints**

Vaccine efficacy is defined as  $VE = 1 - RR$ , where RR is the relative risk in SA4Ag compared to placebo, ie, the proportion of SA4Ag recipients meeting the primary endpoint relative to the proportion of placebo recipients meeting the primary endpoint. Comparing 2 vaccine groups in number of cases may be restated as a 1-sample test of proportions (Chow et al). Let  $x$  = number of SA4Ag cases,  $y$  = number of placebo cases, and total cases  $n=x+y$ . Under the null hypothesis and given the small incidence of cases (1.4% or less expected in the study), then  $x$  has a binomial distribution with probability parameter 0.444 and number of trials  $n$ . Given observed values for  $x$  and  $n$ , and defining  $p=x/n$ , then  $VE = 1-(p/[1-p])$ . A confidence level will be calculated for  $p$  using the Clopper-Pearson method. If the CI for  $p$  is  $(p_L, p_U)$ , then the corresponding CI for VE is  $(1-[p_U/\{1-p_U\}], 1-[p_L/\{1-p_L\}])$ .

A sequential analysis will be performed on the primary endpoint in the PP efficacy population. Early stopping boundaries are based on a group-sequential design (utilizing single-sample binomial distribution, conditional on the total number of cases in both vaccine groups). The parameters of the group-sequential design were calculated based on 1 interim analysis at 50% of information and O'Brien-Fleming-type  $\alpha$ - and  $\beta$ -spending functions. The first-stage probability for rejecting the null hypothesis is 0.0015, and 1-sided probability of rejecting the null hypothesis at the final stage is 0.0245. One-sided probability of 0.0015 corresponds to a 2-sided confidence level of 99.7%, so a 99.7% CI will be calculated for the interim VE estimate. One-sided probability of 0.0245 corresponds to a 2-sided confidence level of 95.1%, so a 95.1% CI will be calculated for the final VE estimate.

The interim analysis will be performed on the first 24 PP cases and the final analysis will be performed on the first 48 PP cases. Although the final analysis is expected to have 48 cases, it is possible that additional potential cases will be present in the adjudication system (entered into the adjudication electronic case report form [eCRF]) on the same day that the 48th per-protocol case is reported to the EAC. These additional cases will be included in the final analysis, if confirmed as cases by the EAC. Therefore, the time order of case notification from the EAC to the sponsor will determine which cases will be included in the analysis. O'Brien-Fleming boundaries will be maintained for decisions regarding VE.

O'Brien-Fleming boundaries will also be maintained if the EAC informs the sponsor of the 25th case (or any further cases) on the same day. It is possible that additional potential cases will be present in the adjudication system. The time order of case notification from the EAC to the sponsor will determine which cases will be included in the interim analysis. Even if more than 24 cases are included in the interim analysis, the final analysis will be performed on 48 cases, unless additional cases are available as described in this section.

The interim analysis will not be revised even if the interim and final case counts do not meet planned values; eg, if the interim analysis is performed with 24 cases, but the final PP analysis has 49 or more cases, the interim analysis will not be revised.

Only the primary endpoint in the PP efficacy population will be subjected to an interim analysis.

The futility analysis will be applied to the primary endpoint only, in the PP efficacy population. After accumulating approximately 10, 15, and 24 primary endpoint cases, the power of the study to reject the original null hypothesis, conditional upon the results accumulated so far, will be calculated. Futility may be declared and the study may cease enrollment, if the conditional power falls below 20%. This will occur if 7 or more vaccine cases are observed out of 10 total cases at the first futility check, or if 9 or more vaccine cases are observed out of 15 total cases at the second futility check, or if 11 or more vaccine cases are observed out of 24 total cases at the third futility check.

The operating characteristics of this futility procedure were explored by simulation. Table 11 displays simulated trial outcomes under a variety of assumptions about the true vaccine efficacy. Under the alternative hypothesis of 70% vaccine efficacy, the futility rule has a low probability of being passed. Conversely, if vaccine efficacy is zero, the chosen futility rule will terminate the study with > 73% probability.

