Once 48 per-protocol cases have accumulated SA4Ag will be compared to placebo for the primary endpoint, testing the hypotheses $H_0: VE \leq 20\%$ vs $H_a: VE > 20\%$. SA4Ag will be deemed efficacious if it has 14 cases or fewer out of a total of 48 cases (point estimate of $VE = 58.8\%$ and 2-sided lower 95.1% confidence limit $> 20\%$).

Although the final analysis is expected to have 48 cases, it is possible that additional potential cases will be present in the adjudication system (entered into the adjudication electronic case report form [eCRF]) on the same day that the 48th per-protocol case is reported to the EAC. These additional cases will be included in the final analysis, if confirmed as cases by the EAC. Therefore, the time order of case entry into the adjudication system will determine which cases will be included in the analysis. O'Brien-Fleming boundaries will be maintained for decisions regarding VE. In other words, in the event that more than 48 cases are available for the final analysis, the null hypothesis will be rejected if the lower bound of the 95.1% confidence interval is greater than 20%.

Similarly, although the interim analysis is expected to have 24 cases, it is possible that additional potential cases will be present in the adjudication system (entered into the adjudication eCRF) on the same day that the 24th per-protocol case is reported to the EAC. These additional cases will be included in the interim analysis, if confirmed as cases by the EAC. The time order of case entry into the adjudication system will determine which cases will be included in the interim analysis. O'Brien-Fleming boundaries will be maintained for decisions regarding VE. In other words, in the event that more than 24 cases are available for the interim analysis, the null hypothesis will be rejected if the lower bound of the 99.7% confidence interval is greater than 20%. Even if more than 24 cases are included in the interim analysis, the final analysis will be performed on 48 cases, unless additional cases are available as described in this section. Similar rules for case inclusion will apply to the futility analyses planned at 10 and 15 per-protocol cases.

No multiplicity adjustments will be applied to the secondary endpoints. All other secondary endpoints will be evaluated at a 2-sided alpha level of 0.05.

[figure not shown]

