9.3.3. Analysis of Secondary Endpoints

9.3.3.1. Efficacy

All secondary endpoints will be analyzed using the per-protocol population. The binomial methodology described above will be used to test the null hypothesis of no difference between treatments, with $p = 1/2$ and number of trials set to total number of cases from SA4Ag and placebo. Two-sided p-values of the probability of the indicated SA4Ag cases or fewer will be calculated.

As sensitivity analyses, the secondary endpoints will be evaluated in the mITT populations with $p = 1/2$ and number of trials set to total number of cases from SA4Ag and placebo.

Secondary endpoints will be analyzed only after all subjects have completed the study and the database is locked.

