## 4. HYPOTHESES AND DECISION RULES

### 4.1. Statistical Hypotheses

SA4Ag will be compared to placebo testing the hypotheses  $H_0: VE \leq 20\%$  vs  $H_a: VE > 20\%$ .

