**Table 11. Operating Characteristics of Study Design**

Study Outcome	Assumed Vaccine Efficacy (%)			
	0%	20%	60%	70%
Futility				
at 10 cases	17.0%	9.6%	0.7%	0.2%
at 15 cases	15.7%	9.5%	0.7%	0.2%
at 24 cases	40.9%	34.3%	4.4%	1.0%
at any time	73.6%	53.3%	5.9%	1.4%
Positive Interim Analysis	0.0%	0.1%	5.8%	16.3%
Positive Final Analysis	0.3%	2.2%	54.7%	71.2%
Negative Final Analysis	26.1%	44.4%	33.6%	11.1%
Total Positive Outcomes	0.3%	2.3%	60.5%	87.5%
Total Negative Outcomes	99.7%	97.7%	39.5%	12.5%
Mean no. cases required	26.5	33.0	45.0	43.7

Percentages of study outcomes in 100,000 simulations of the trial under each assumed vaccine efficacy. ‘Positive’ outcomes are where the null hypothesis that VE ≤20% is rejected at either the interim or final analysis. ‘Negative’ outcomes are a declaration of futility or failing to reject the null hypothesis at the final analysis. All percentages rounded to 0.1%.

The analyses of the secondary endpoints, the exploratory efficacy endpoints, and the primary endpoint in the mITT efficacy population will be evaluated at a 2-sided alpha level of 0.05. The proportion of SA4Ag cases divided by total cases will be translated into VE for each endpoint. The upper and lower limits of the associated 95% CI on the proportion will be translated to upper and lower 95% confidence limits on VE.

Subgroup analyses will use the same methodology as described above, but will be performed separately at each level of the subgroup. Some levels of subgroups may be combined before analysis. Subgroups without cases in either vaccine group will not be analyzed.

The subgroup analyses on the primary endpoint from the PP efficacy population will be performed on the 24 cases (if the study ends on interim analysis) or 48 cases (if the study ends as planned). More PP cases may accumulate after the 24 or 48 cases as remaining subjects complete enrollment, so the subgroup analyses will also be repeated with the additional cases.

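### The SAP names no null hypothesis for the secondary, exploratory and mITT efficacy tests, and the protocol's two-sided p-value for secondary endpoints is worded as a lower tail

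*SAP*

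**What the plan says.** **Protocol.** Section 9.1 sets the primary null at VE of 20% or less and says of the rest: "All other secondary endpoints will be evaluated at a 2-sided alpha level of 0.05", without multiplicity adjustment. For secondary endpoints, Section 9.3.3.1 says that the binomial method "will be used to test the null hypothesis of no difference between treatments", with p = 1/2. It uses p = 1/2 again for those endpoints in the mITT populations, as sensitivity analyses. On the p-value it says: "Two-sided p-values of the probability of the indicated SA4Ag cases or fewer will be calculated".

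**SAP.** Section 4.1 gives a single pair of hypotheses, introduced by "SA4Ag will be compared to placebo testing the hypotheses", with the null at VE of 20% or less. Section 8.1.1, the methodology for efficacy endpoints, says that under the null the number of SA4Ag cases "has a binomial distribution with probability parameter 0.444 and number of trials" n. After Table 11 it continues: "The analyses of the secondary endpoints, the exploratory efficacy endpoints, and the primary endpoint in the mITT efficacy population will be evaluated". The level given there is 0.05, two-sided, and a 95% interval for the case proportion is converted to VE. The text at that point names no null value and defines no p-value. Tables 14 and 15 list the method as binomial for every endpoint. Table 15 labels the primary endpoint in the mITT populations as a secondary efficacy endpoint. The value 1/2 appears nowhere in the SAP as a test null.

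**The concern.** A programmer working from the SAP has one binomial parameter to hand, 0.444. One working from the protocol would use 1/2 for secondary endpoints. Both would be running the binomial test at a 2-sided 0.05, and for some counts one would reject and the other would not.

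The primary endpoint repeated in the mITT populations is the least clear case. By endpoint it belongs with 0.444. By its Table 15 label, read together with Protocol 9.3.3.1, it could be given 1/2.

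The p-value wording is a second, independent problem. The probability of the observed SA4Ag count or fewer is one tail. Calling it two-sided leaves open whether it is compared with 0.05 as it stands or doubled first. A lower tail also approaches 1 when cases pile up on SA4Ag, so it cannot register an excess there.

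**Working it through.** **Inputs.** 1:1 randomization; primary null proportion 0.444; alternative 0.230; 48 cases; success at 14 or fewer SA4Ag cases (Protocol 9.1 and 9.2). Secondary null proportion 1/2 and 2-sided alpha 0.05 (Protocol 9.1 and 9.3.3.1). Clopper-Pearson intervals, with VE = 1 − p/(1 − p) (SAP 8.1.1). The documents do not state the number of secondary-endpoint cases. I assume 48 and show a range.

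**1. Reproduce the primary design.** P(X ≤ 14 | 48, 0.444) = 0.0224, below the 0.0245 allowed at the final look; P(X ≤ 15 | 48, 0.444) = 0.0441. P(X ≤ 14 | 48, 0.230) = 0.880, against the stated power of 0.88. The 95.1% interval at 14/48 is VE 58.8% (21.0% to 79.6%), as in Protocol Table 15. So 0.444 is the null behind the primary rule, and that rule is sound.

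**2. Rejection limits under each null.** The largest SA4Ag count with a lower tail of at most 0.025:

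| Total cases | Null 1/2 | Null 0.444 |
|---|---|---|
| 24 | 6 | 5 |
| 30 | 9 | 7 |
| 40 | 13 | 11 |
| 48 | 16 | 14 |
| 60 | 21 | 18 |
| 80 | 30 | 26 |
| 100 | 39 | 34 |

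The limits differ at every total tabulated.

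**3. Counts with opposite results at 48 cases.**

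| SA4Ag cases | VE (95% CI) | Doubled lower tail, 1/2 | Doubled lower tail, 0.444 |
|---|---|---|---|
| 14 | 58.8% (21.2% to 79.6%) | 0.0055 | 0.045 |
| 15 | 54.5% (13.9% to 77.1%) | 0.013 | 0.088 |
| 16 | 50.0% (6.2% to 74.4%) | 0.029 | 0.160 |
| 17 | 45.2% (−2.2% to 71.5%) | 0.059 | 0.267 |

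Counts of 15 and 16 reject under 1/2 and not under 0.444.

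**4. Power.** At true VE the SA4Ag share of cases is (1 − VE)/(2 − VE). For VE = 50% that is 0.5/1.5 = 1/3. Then P(X ≤ 16 | 48, 1/3) = 0.567 and P(X ≤ 14 | 48, 1/3) = 0.328. With 60 cases, P(X ≤ 21) = 0.664 and P(X ≤ 18) = 0.346.

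**5. The p-value wording, null 1/2.**
- At 17/48 the lower tail is 0.0297. Compared directly with 0.05 it is significant. Doubled it is 0.059, which is not significant and agrees with the 95% CI, whose lower limit is −2.2%.
- At 32/48 the lower tail is 0.993, or 1 when doubled and capped. The upper tail is P(X ≥ 32) = P(X ≤ 16) = 0.0147, so the exact two-sided p is 0.029. The planned 95% CI for VE is −290% to −6.6%, which excludes zero.

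**The case against.** The strongest reply is that the SAP contains no conflicting rule. The 0.444 sentence sits in text about the primary endpoint, and the sentence on the other analyses never mentions 0.444. Where the SAP is silent, the protocol supplies p = 1/2. That stands as a description: this is a gap, not an explicit second rule. It does not close the gap. The protocol (Section 9) lets the SAP modify the planned analyses, and the SAP's general efficacy section offers one null and one parameter.

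It is also fair that the SAP's stated output for these analyses is VE with a 95% CI, which is the same under either null; that secondary endpoints carry no multiplicity control and do not decide the trial; and that SAP 8.1.3.5 records that the study met its futility criteria in December 2018. These points limit the consequence. But a 2-sided alpha implies a test, and the SAP does not say which VE value the interval is compared with. Its missing-data step (Section 7) tabulates lower limits above 0%, 20% and 30% without naming the deciding one.

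Three stronger readings are not supported:
- **The plan cannot detect harm.** Only the literal lower-tail p-value is blind to it. The planned two-sided interval shows it, as at 32/48.
- **Testing against 0.444 would flag false harm when VE is 0.** At true VE = 0 the null of 20% is false, so an upper-tail rejection is a correct one. It indicates VE below 20%, not harm. At 29/48, the smallest count that would do this, the 95% CI is −188% to 17% and includes zero.
- **The mITT check of the primary endpoint is set at a lower bar.** Using 1/2 there would declare success 7.9% of the time at true VE = 20%, since P(X ≤ 16 | 48, 4/9) = 0.079. But the protocol applies 1/2 in mITT to the secondary endpoints only. The figure shows what one reading of the Table 15 label would do, not what the plan directs.

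**Conclusion.** The concern holds as a specification gap with a real numerical consequence. The protocol gives p = 1/2 for secondary endpoints; the SAP supplies only 0.444 and names no null for the secondary, exploratory and mITT-primary tests. With 48 cases the limits are 16 and 14 SA4Ag cases, and power at a true VE of 50% is 57% or 33%. These figures rest on the assumed 48 cases, but the limits differ at every total tabulated from 24 to 100. Separately, the protocol's p-value sentence contradicts itself. Its literal value disagrees with the planned interval at 17/48 and misses an excess on SA4Ag at 32/48.

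The per-protocol primary test uses 0.444 in both documents and reproduces. Nothing here changes it or the futility outcome.

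**What to change.** - **SAP 4.1, 8.1.1 and Tables 14 and 15:** state that secondary and exploratory efficacy endpoints are tested against p = 1/2 (VE = 0), equivalently that the 95% CI for VE excludes 0%. State that the primary endpoint keeps the 0.444 null when repeated in the mITT and restricted mITT populations.
- **Protocol 9.3.3.1 and the SAP:** define the two-sided p-value as twice the smaller exact binomial tail, capped at 1. This agrees with the Clopper-Pearson interval already planned.

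The cost is a few sentences in each document and no new data. The one downside is that the mITT analysis of the primary endpoint faces a slightly stricter bar than p = 1/2 would set: 14 rather than 16 cases if there were 48.
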